**Evaluation of Overall Response:**

Target Lesion	Non-target lesion	New Lesion	Objective Status
CR	CR	No	CR
CR	Non-CR/ Non-PD	No	PR
CR	Indeterminate or missing	No	PR
PR	Non-CR/ Non-PD, Indeterminate or missing	No	PR
SD	Non-CR/ Non-PD, Indeterminate or missing	No	SD
Indeterminate or missing	Non-PD	No	Indeterminate
PD	Any	Yes or no	PD
Any	PD	Yes or no	PD
Any	Any	Yes	PD

CR=complete response; PR=partial response; SD=stable disease; PD= progression; non-CR/non-PD=criteria for neither CR nor PD have been met.

All noted regressions should be confirmed at next tumor assessment.

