### 6.1 Overall Study Design

The ADU-CL-20 study is an open-label, multicenter Phase 2 clinical trial to evaluate the efficacy and safety of intratumoral ADU-S100 (also referred to as MIW815) administered with standard of care treatment (ie, pembrolizumab) in the first-line setting. The multicenter clinical trial will be conducted at approximately 25 sites in North America. Twenty evaluable subjects will initially be enrolled. If the total number responding is greater than or equal to 4, then an additional 14 evaluable subjects will be enrolled in the second stage for a total of 34 evaluable subjects.

The population for this study will consist of adults with metastatic head and neck squamous cell cancer (HNSCC) where pembrolizumab is indicated as the standard of care first line treatment. Individuals with intercurrent illnesses, inadequate organ function, various conditions impacting immune function, or other mitigating factors as detailed in the exclusion criteria will not be enrolled as these factors may interfere with the proposed mode of action of ADU-S100 and pembrolizumab, introduce undue safety risks, or confound interpretation of study results.

The trial design consists of a Screening Period, Treatment Period, and a Follow-up Period as depicted in [Figure 1](#). Screening assessments will be conducted to confirm eligibility and to obtain baseline (pre-treatment) measurements. Screening must be completed within 28 days prior to the first dose of either study drug. An enrollment form will confirm subject eligibility; baseline biopsies will not be performed until enrollment is confirmed. All eligible subjects will receive intravenous (IV) infusions of pembrolizumab (200 mg) and intratumoral injections of ADU-S100 (800 mcg/lesion; up to 2 lesions). During the Treatment Period, study medications will be administered in 21-day dosing cycles until criteria for treatment discontinuation are met, or up to 35 cycles. Tumor responses will be evaluated at 9-week intervals. The Follow-up Period is designed to assess vital status, subsequent anti-cancer therapy, and complete safety reporting requirements.

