## 6.5 **Efficacy and Safety Variables**

### 6.5.1 *Efficacy Variables*

#### 6.5.1.1 *Primary Efficacy Variable*

The primary efficacy endpoint is the objective response rate (ORR) defined as the proportion of subjects in whom a complete response (CR) or a partial response (PR) is observed. The Response Evaluation Criteria in Solid Tumors (RECIST) v1.1 will be used to evaluate the primary efficacy endpoint. All responses will be confirmed at the subsequent tumor assessment.

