- Duration of Disease Control (DODC): defined as the time from the first tumor assessment that supports the subject's disease control (CR, PR, SD) to the time of disease progression or death due to any cause; if the subject has a best response of SD, then DODC is calculated from date of baseline tumor assessment to the time of disease progression or death due to any cause. For subjects who have ongoing disease control at the time of analysis, their DODC will be censored at the time of last evaluable tumor assessment. Subjects who receive anti-cancer therapy prior to documented disease progression will be censored on the date of last evaluable tumor assessment on or prior to the start date of the anti-cancer therapy. Subjects with no on-treatment tumor assessments will be censored on the date of treatment start.
- ORR per modified RECIST v1.1 for immune-based therapeutics (iRECIST), where all noted disease progression will be confirmed at the subsequent tumor assessment
- Occurrence and severity of treatment-emergent adverse events
- Changes from baseline in safety assessments
- Plasma concentration-time profiles and derived noncompartmental PK parameters (including  $C_{max}$ , area under curve [AUC])

Progression-free survival, DOR, DCR, and DODC will be determined per RECIST v1.1 and iRECIST. [Section 7.4.6.2](#) contains a full table of the censoring rules that will be used in these analyses. [Section 7.4.6.3](#) contains additional information regarding response assessment per iRECIST. [Section 7.4.6.8](#) contains additional information regarding subgroup analysis.

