#### 7.4.6.3 iRECIST Response Assessment

iRECIST is based on RECIST criteria. There are no changes compared to RECIST to the recommendations regarding the method of measurement. All responses per iRECIST have a prefix of “i” (ie, immune)—eg, “immune” complete response (iCR) or partial response (iPR),

and unconfirmed progressive disease (iUPD) or confirmed progressive disease (iCPD) to differentiate them from responses assigned using RECIST 1.1. Similar nomenclature is used for stable disease (iSD).

The iRECIST response assessment allows for the occurrence of pseudoprogression where a subject may appear to worsen before a delayed response occurs. Thus, instances of iRECIST progressive disease require confirmation. That is, if iUPD is not confirmed as iCPD, then the response effectively resets with the next iRECIST evaluation. In the event that no further response assessment follows the iUPD assessment (eg, subject was not judged to be clinically stable or subject refusal, protocol noncompliance, or death) or if all subsequent timepoint responses are iUPD, then date of iUPD can be used for analysis. Several examples of assignments of best overall response using iRECIST, are presented in [Table 4](#), adapted from the RECIST working group guidelines ([Seymour et al. 2017](#)).

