**Table 4 Scenarios of Assignments of Best Overall Response using iRECIST**

	Timepoint Response 1	Timepoint Response 2	Timepoint Response 3	Timepoint Response 4	Timepoint Response 5	iBOR
Ex. 1	iCR	iCR, iUPD, or NE	iCR, iUPD, or NE	iUPD	iCPD	iCR
Ex. 2	iUPD	iPR, iSD, or NE	iCR	iCR, iUPD, or NE	iCR, iPR, iSD, iUPD, iCPD, or NE	iCR
Ex. 3	iUPD	iPR	iPR, iSD, iUPD, or NE	iPR, iSD, iUPD, NE, or iCPD	iPR, iSD, iUPD, NE, or iCPD	iPR
Ex. 4	iUPD	iSD or NE	iPR	iPR, iSD, iUPD, or NE	iPR, iSD, iUPD, iCPD, NE	iPR
Ex. 5	iUPD	iSD	iSD, iUPD, or NE	iSD, iUPD, iCPD, or NE	iSD, iUPD, iCPD, NE	iSD
Ex. 6	iUPD	iCPD	Any	Any	Any	iCPD
Ex. 7	iUPD	iUPD (no iCPD)	iCPD	Any	Any	iCPD
Ex. 8	iUPD	NE	NE	NE	NE	iUPD

Abbreviations for Table 4: iBOR = immune best overall response; iCPD = immune confirmed progressive disease; iCR = immune complete response; iPR = immune partial response; iSD = immune stable disease; iUPD = immune unconfirmed progressive disease; NE = not evaluable

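### The iRECIST ORR can exceed the RECIST ORR through missing response confirmation alone, because the SAP confirms responses under RECIST but only progression under iRECIST

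*SAP*

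**What the plan says.** **RECIST v1.1 (primary).** SAP 6.5.1.1 gives ORR as "defined as the proportion of subjects in whom a complete response (CR) or a partial response (PR) is observed" and then adds "All responses will be confirmed at the subsequent tumor assessment". Protocol Appendix B agrees, under the overall response table: "All noted regressions should be confirmed at next tumor assessment".

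**iRECIST (secondary).** SAP 6.5.1.2 lists ORR per iRECIST, "where all noted disease progression will be confirmed at the subsequent tumor assessment". It refers the reader to SAP 7.4.6.3 for response assessment, where the rule again concerns progression only: "Thus, instances of iRECIST progressive disease require confirmation". Protocol Appendix C sets out how progression is confirmed and has no matching requirement for iCR or iPR.

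**Table 4 (best overall response under iRECIST).**
- Example 1 starts with iCR. Timepoints 2 and 3 may each be iCR, iUPD or NE; then come iUPD and iCPD. The result is iCR.
- Example 3 has iUPD, then iPR, then "iPR, iSD, iUPD, or NE" at timepoint 3, with iCPD also allowed later. The result is iPR.
- Example 4 has its iPR at timepoint 3, after iUPD and then iSD or NE. Later timepoints need not repeat the iPR. The result is iPR.

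**Why iRECIST is used.** SAP 7.4.6.3 states: "The iRECIST response assessment allows for the occurrence of pseudoprogression where a subject may appear to worsen before a delayed response occurs".

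**The concern.** Readers will set the two ORRs side by side. Given the stated purpose of iRECIST, they will take any excess of the iRECIST rate over the RECIST rate as late response after apparent progression. That reading is sound only if the two rates define a response in the same way apart from the handling of progression. Here they also differ on confirmation, so part or all of an excess may come from responses that were seen once and never confirmed.

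The same mismatch reaches duration of response, which SAP 6.5.1.2 reports under both criteria. A subject with one unconfirmed response would enter the iRECIST duration set but not the RECIST set.

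**Working it through.** The plan gives no figure for the difference between the two ORRs, so there is none to reproduce. The check has four steps.

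**1. One permitted sequence under both rules.** Take Table 4 Example 1 as iCR, NE, NE, iUPD, iCPD.
- iRECIST: Table 4 gives iCR, a responder.
- RECIST v1.1: a CR with no evaluable scan after it until progression is not confirmed at the next assessment, so it fails SAP 6.5.1.1.
- No iUPD precedes the iCR, so pseudoprogression plays no part in the discordance.

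**2. How much of Table 4 rests on a single response.** These are counts of the sequences each example permits, and of those with exactly one iCR or iPR. They are counts of table paths, not probabilities.

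| Example | Permitted sequences | Exactly one iCR/iPR | iUPD before the response? |
|---|---|---|---|
| 1 | 3 × 3 = 9 | 2 × 2 = 4 | No |
| 3 | 4 × 5 × 5 = 100 | 3 × 4 × 4 = 48 | Yes |
| 4 | 2 × 4 × 5 = 40 | 2 × 3 × 4 = 24 | Yes |

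All three show that iRECIST response confirmation is not required. Only Example 1 shows it without a preceding iUPD.

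**3. Size of the gap from confirmation alone.** Let p be the rate of any noted response and u the share of noted responses not confirmed. With no pseudoprogression, iRECIST ORR = p and RECIST ORR = p(1 − u), so the expected gap is p × u. The chance of at least one discordant subject among n is 1 − (1 − pu)^n.

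Inputs:
- p = 0.19 and 0.38, the null and alternative rates in SAP 6.2 and Protocol 12.1, used here only as a range.
- u = 5% to 30%, my assumption; the documents give no value.
- n = 20, from Protocol 12.1 (about 20 evaluable subjects).

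| p | u | Gap (points) | Expected subjects of 20 | Chance of at least one |
|---|---|---|---|---|
| 0.19 | 5% | 1.0 | 0.19 | 17% |
| 0.19 | 10% | 1.9 | 0.38 | 32% |
| 0.19 | 20% | 3.8 | 0.76 | 54% |
| 0.19 | 30% | 5.7 | 1.14 | 69% |
| 0.38 | 5% | 1.9 | 0.38 | 32% |
| 0.38 | 10% | 3.8 | 0.76 | 54% |
| 0.38 | 20% | 7.6 | 1.52 | 79% |
| 0.38 | 30% | 11.4 | 2.28 | 91% |

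Observed gaps come in whole subjects, and 1/20 = 5 points. With one confirmation rule for both criteria, the gap from this source is 0.

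**4. Can a confirming scan be missed?** Yes.
- SAP 6.1 states: "Tumor responses will be evaluated at 9-week intervals".
- Protocol 7.1 and 9.4.2.3 send a subject to the EOT visit when regression leaves no lesion that can be injected.
- EOT falls 30 (+7) days after the last dose. Protocol Table 2-1 asks for imaging at EOT only if more than 6 weeks (42 days) have passed since the last evaluation. If the last dose is on or before the day of the response scan, EOT comes at most 37 days after that scan, so no EOT scan is triggered.

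**The case against.** The case on the other side has several parts.

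- **The RECIST rule is not airtight.** SAP 6.5.1.1 speaks of a response being observed as well as confirmed, and no passage says how an unconfirmed CR or PR is classified. If RECIST ORR were programmed on any observed response, the asymmetry would vanish. That is true, but it would set aside the confirmation sentence in the same paragraph. The missing classification stands as a gap, and the fix covers it.
- **The iRECIST rule is partly inferred.** The SAP never says outright that iRECIST ORR is the share with a best overall response of iCR or iPR. It calls Table 4 a set of examples, and it bases iRECIST on RECIST, so response confirmation might be thought to carry over. Table 4 contradicts that carry-over, and SAP 6.5.1.2 points to the section that contains it. The statement that nothing changes from RECIST concerns only the method of measurement.
- **Examples 3 and 4 start with iUPD.** They depict the delayed response that iRECIST is meant to capture. This stands: the claim of a gap without pseudoprogression rests on Example 1.
- **The EOT route is narrow.** It applies only when no lesion can be injected, and other lesions may be selected first. SAP 6.1 also asks for continued tumor assessment after stopping for reasons other than progression, although the current protocol schedule no longer shows that follow-up. This stands as a limit on how often confirmation is lost.
- **The consequence is modest.** SAP 7.4.6.6 describes results as descriptive with no formal comparisons. Swimmer plots under both criteria and subject listings would let a careful reader find discordant subjects. This also stands.

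**Conclusion.** The concern holds as a difference in definition. Followed as written, the SAP requires confirmation of CR and PR under RECIST v1.1 and does not require it of iCR and iPR. The iRECIST ORR can then be the larger of the two through missing confirmation alone, whenever at least one response is unconfirmed. Under the assumed ranges the expected gap is 1.0 to 11.4 points; these figures depend wholly on the assumed unconfirmed share.

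A reader might infer three stronger things that the documents do not support:
- **That the iRECIST ORR must exceed the RECIST ORR.** If every response is confirmed, this source adds nothing. At p = 0.19 and u = 5%, the chance of no discordant subject among 20 is 83%.
- **That any observed excess is an artefact.** Genuine late responses after iUPD would also produce one, and the plan as written does not separate the two.
- **That the primary result is at risk.** The primary ORR does not use the iRECIST rule, no test of the difference is planned, and no error rate changes.

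What is affected is the descriptive interpretation of the iRECIST ORR and of duration of response per iRECIST.

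**What to change.** Before the SAP is finalized:

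1. State one confirmation rule in SAP 6.5.1.1 and 6.5.1.2 that applies equally to CR/PR and iCR/iPR.
2. State that a response not confirmed at the subsequent assessment does not count as an objective response under either criterion, and name the category it falls into.
3. Say explicitly that iRECIST ORR is the proportion with a best overall response of iCR or iPR, and align Table 4. For example, an Example 1 subject with one iCR followed only by NE or iUPD is unconfirmed.
4. Report unconfirmed ORR under both criteria as supportive output, so that the effect of confirmation and the effect of pseudoprogression can be read apart.
5. Use the same responder flag to define the duration of response set under each criterion.

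The cost is SAP wording, one derivation flag and a supportive table. No new data are needed. The iRECIST ORR may be slightly lower than under the present rule, and Table 4 will depart from the published examples it was adapted from, which a footnote should say.

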## **6.5.2 Description of Safety Variables**

Safety will be assessed by collection of data on treatment-emergent adverse events (TEAEs), Eastern Cooperative Oncology Group (ECOG) performance status, vital signs, weight, physical examination, electrocardiogram (ECG) parameters, concomitant medications, and routine clinical laboratory assessments. Clinically significant changes from pre-treatment values in safety assessments will be reported as adverse events (AEs). Safety assessments described below will be conducted according to [Appendix A: Schedule of Events](#).

### **6.5.2.1 Adverse Events**

An AE is defined as any untoward medical occurrence associated with the use of a drug in humans, whether or not considered drug-related. An AE can therefore be any unfavorable and/or unintended sign (including an abnormal laboratory finding), symptom, or disease temporally associated with the use of an investigational medicinal product, whether or not related to the investigational medicinal product.

See Section 11.1.2 of the study Protocol for further details regarding the definition of AEs.

#### 6.5.2.2 *Serious Adverse Events*

An AE or adverse reaction is considered serious if, in the view of either the Investigator or Sponsor, it results in any of the following outcomes:

- Death
- A life-threatening AE
- Requires hospitalization or prolongation of existing hospitalization
- A persistent or significant incapacity or substantial disruption of the ability to conduct normal life functions
- A congenital anomaly/birth defect
- An important medical event

See Section 11.2 and 11.3 of the study Protocol for further details regarding serious adverse events (SAEs) and reporting.

#### 6.5.2.3 *Eastern Cooperative Oncology Group (ECOG) Scale of Performance Status*

The ECOG Scale of Performance Status is recognized as a standard tool to measure disease impact on daily living activities (Oken et al. 1982). The ECOG scale will be used by site personnel to determine eligibility and characterize a subject's level of functioning (self-care, daily activity, and basic physical ability) as indicated in [Appendix A: Schedule of Events](#).

The ECOG performance status will be classified according to the following categories:

- 0; Fully active, able to carry on all pre-disease performance without restriction
- 1; Restricted in physically strenuous activity but ambulatory and able to carry out work of a light or sedentary nature, eg, light house work, office work
- 2; Ambulatory and capable of all self-care but unable to carry out any work activities. Up and about more than 50% of waking hours
- 3; Capable of only limited self-care, confined to bed or chair more than 50% of waking hours
- 4; Completely disabled. Cannot carry on any self-care. Totally confined to bed or chair

- 5; Dead

#### 6.5.2.4 *Vital Signs*

Vital signs, including blood pressure, pulse rate, respiratory rate, and temperature will be obtained at each indicated visit (prior to dosing, as applicable). Serial time points following ADU-S100 administration support monitoring for cytokine release syndrome (CRS) during Cycle 1. Vital signs will be collected prior to dosing and as indicated in [Appendix A: Schedule of Events](#). Additional measurements will be obtained if clinically indicated.

#### 6.5.2.5 *Comprehensive Physical Examination*

Comprehensive physical examinations will be conducted at Screening and EOT. The comprehensive physical examination will include the following organ or body system assessments: skin; head, eyes, ears, nose, and throat; thyroid; lungs; cardiovascular system; abdomen (liver and spleen); extremities; lymph nodes; and a brief neurological examination.

#### 6.5.2.6 *Symptom-directed Physical Examination*

Symptom-directed physical examinations may be conducted at all other visits as indicated (up to 3 days prior to dosing). The Investigator or medically licensed designee will perform a symptom-directed evaluation as clinically indicated, including assessment(s) of the body systems or organs based on a subject's symptoms, AEs, or other findings.

#### 6.5.2.7 *Weight*

Weight (kg) will be obtained at each indicated visit (prior to dosing, if applicable).

#### 6.5.2.8 *Electrocardiogram (ECG)*

At screening and during the study, triplicate ECG assessments will be performed with local 12-lead ECG equipment according to standard procedures to determine the corrected QT interval calculated by Fridericia's formula (QTcF). At screening, the average value of the triplicate will be utilized for enrollment into the study.

The triplicates will be performed no less than 3 minutes apart and within approximately 30 minutes of the initial ECG to determine the mean QTcF interval. All 12-lead ECGs should be performed after the subject has rested in a recumbent or semi-recumbent position for  $\geq 5$  minutes. Additional ECGs may also be performed throughout the study if clinically indicated. The ECGs will be performed prior to study drug administration for all pre-dose assessments. If blood sampling or vital sign measurement is scheduled for the same visit as an ECG recording, the procedures will be performed in the following order: ECG, vital signs, blood draw.

ECG parameters to be evaluated include heart rate, PR interval, QT interval, QRS duration, and QTcF.

The ECG will be interpreted by the Investigator as normal, not clinically significant abnormal, or clinically significant abnormal. If the mean QTcF is prolonged (ie, > 500 msec, or CTCAE Grade 3) or if the mean change from baseline is  $\geq 60$  msec, the ECGs will be reevaluated by a qualified person.

#### 6.5.2.9 *Prior and Concomitant Medications*

Medications used within 28 days prior to the first dose of ADU-S100 will be recorded as prior medications.

Concomitant medications include pre-medications and all prescription, over the counter medications, herbal remedies and dietary supplements administered from Cycle 1 Day 1 until the EOT visit. The generic name, dosage, duration, and reason for the concomitant medication will be documented. If a subject is using biotin supplements (found in multivitamins, biotin supplements, and supplements for hair, skin, and nail growth), these will also be noted for laboratory assessments. Changes in the use of concomitant medications will be captured at each study visit.

Following the EOT visit, concomitant medications will only be collected if associated with the management of an ongoing AE or SAE, or if a new anti-cancer treatment.

#### 6.5.2.10 *Screening-Specific Laboratory Assessments*

Blood and urine samples will be obtained at screening to confirm eligibility for each subject. These initial laboratory assessments will be conducted at the institution's local laboratory:

- Virology/Serology Screen: human immunodeficiency virus (HIV) antibody, hepatitis B (HBV) surface antigen, hepatitis C (HCV) antibody, HCV viral load (if indicated), Epstein-Barr virus (EBV) (Epstein-Barr nuclear antigen [EBNA], viral capsid antigen [VCA] immunoglobulin G [IgG], VCA immunoglobulin M [IgM], EBV polymerase chain reaction [PCR] as clinically indicated)
- Urinalysis (dipstick or automated analysis): bilirubin, blood, glucose, ketones, leukocytes, nitrite, pH, protein, and specific gravity
  - If dipstick result is abnormal, microscopy will be used to measure sediment (red blood cells, white blood cells, epithelial cells, crystals, casts, bacteria)
  - Additional urinalysis may be performed throughout the study if clinically indicated

#### 6.5.2.11 *Safety Laboratory Assessments*

Routine hematology, serum chemistry, coagulation panel, and thyroid function testing will be conducted to assess eligibility and as a measure of safety throughout the study per protocol requirements. All clinical laboratory evaluations will be performed by the institution's local laboratory. Laboratory assessments for continued dosing of pembrolizumab must be confirmed prior to dosing; testing may be completed up to 3 days prior to study drug administration for each cycle. Fasting is not required; however fasting blood glucose will be performed if clinically indicated.

The following parameters will be evaluated:

- Hematology: complete blood count (hematocrit, hemoglobin, platelets, red blood cells, white blood cells with differential [absolute counts: basophils, eosinophils, lymphocytes, monocytes, neutrophils])
- Serum chemistry: albumin, alkaline phosphatase, alanine aminotransferase (ALT), aspartate aminotransferase (AST), bicarbonate, calcium, chloride, lactate dehydrogenase, sodium, potassium, creatinine, glucose, magnesium, phosphate (inorganic phosphorus), bilirubin (total, direct), blood urea nitrogen, uric acid, total protein
- Coagulation panel: prothrombin time, international normalized ratio of prothrombin time, activated partial thromboplastin time
- Thyroid function: thyroid stimulating hormone (TSH), free tri-iodothyronine (FT3), free thyroxine (FT4)

